10.3 POPULATION FOR ANALYSIS

10.3.1 Evaluable for toxicity:

All patients will be evaluable for toxicity from the time of their first treatment with lenalidomide, romidepsin and CC-486 (5-azacitidine).

10.3.2 Evaluable for objective response:

Only those patients who have measurable disease present at baseline, have received at least one cycle of therapy, and have had their disease re-evaluated will be considered evaluable for response. These patients will have their response classified according to the definitions stated above, Section **6.3.** (NOTE: Patients who exhibit objective disease progression prior to the end of Cycle 1 will also be considered evaluable.)

10.3.3 Evaluable Non-Target Disease Response:

Patients who have lesions present at baseline that are evaluable but do not meet the definitions of measurable disease, have received at least one cycle of therapy, and have had their disease re-evaluated will be considered evaluable for non-target disease. The response assessment is based on the presence, absence, or unequivocal progression of the lesions.

10.3.4 Evaluable for DLT:

All participants who either completed cycle 1 treatment or experienced a DLT during cycle 1 will be evaluable for DLT. If a participant did not experience DLT and did not finish cycle 1 treatment, they will not be evaluable for toxicity and will be replaced in the dose level.

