3.2 DOSE LIMITING TOXICITY

A dose-limiting toxicity (DLT) is defined as: any treatment-emergent and related severe (grade \geq 3) toxicity, i.e., toxicity deemed related to lenalidomide, romidepsin and/or CC-486 (5-azacitidine) by the PI or designee and occurring during the MTD observation time, defined as day -7 until end of cycle 1 (normally day 22). Each patient must receive all doses of the investigational medications during cycle 1 to be considered as successfully completing the DLT evaluation period.

The following toxicities and conditions will be recorded, however they will not be considered to be DLTs:

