10 STATISTICAL CONSIDERATIONS

10.1 STATISTICAL HYPOTHESIS

- Primary Endpoint(s):
 - Maximum tolerated dose (MTD) of lenalidomide administered orally in combination with romidepsin and CC-486 (5-azacitidine) for up to 6 cycles
 - Frequency (number and percentage) of treatment-emergent AEs
- Secondary Endpoint(s):
 - Overall response rate (including complete response rate and partial response rate), after treatment
 - Duration of response, after treatment
 - Progression-free survival after treatment
 - Event-free survival after treatment
 - Overall survival

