10.2 SAMPLE SIZE DETERMINATION

The MTD will be based on the assessment of DLT during the first cycle of treatment and will be defined as the dose level at which less than one-third of patients (0 of 3 or 0-1 of 6 patients) treated experience a DLT, with the next higher dose level demonstrating one-third or a greater number of patients (≥ 2 of 3 or ≥ 2 of 6 patients) having a DLT. If a subject did not experience a DLT and did not finish one cycle of treatment (21 days) they will not be evaluable for determination of the MTD and would be replaced in the dose level. An additional 3 to 6 patients will be enrolled at the MTD, so that a total of 9 patients will be treated at this dose.

Using this dose-escalation scheme the probability of escalating to the next dose level will be based on the true rate of DLT at the current doses given by the following table (each group will be considered independently of the other); Thus, if the true underlying proportion of DLTs is 50% at the current dose there is a 17% probability of escalating to the next dose.

True toxicity at a given dose	10%	20%	30%	40%	50%	60%
Probability of escalating	0.91	0.71	0.49	0.31	0.17	0.08

If all four dose levels are evaluated with 6 patients per dose level and 9 total patients at the MTD, a maximum of 27 evaluable patients will be enrolled. Similarly, if all dose levels are evaluated with 3 patients per dose level and 9 total patients at the MTD, the minimum number of evaluable patients required will be 18. To account of unevaluable patients, accrual ceiling will be set at 36. It is expected that the accrual can be completed in 29 months.

A maximum of 30 patients will be enrolled over 29 months, at a rate of 1-2 patients per month.

After execution of amendment 12/07/2022, we will no longer enroll into the original Arm 2 expansion cohort and will test a new modified dose-expansion arm removing the lenalidomide lead-in window and expanding the cycle length to 28 days to enroll the remaining participants.

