10.4.2 Analysis of the Primary Endpoints

Safety summaries will include summaries in the form of tables and listings. Reports will include the frequency (number and percentage) of treatment emergent AEs grouped by severity of the AE (per CTCAE, v5.0) and by relationship to study drug (e.g., lenalidomide, romidepsin, CC-486 (5-azacitidine) in any combinations).

Laboratory shift tables containing counts and percentages will be prepared by treatment assignment, laboratory parameter, and time. Summary tables will be prepared for each laboratory parameter. Figures of changes in laboratory parameters over time will be generated.

Results of vital sign assessments, ECGs, and physical exams will be tabulated and summarized.

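### Section 10.3.4 says early non-completers without a DLT are not evaluable for toxicity, contradicting 10.3.1 and 10.2 and leaving the denominator of the primary AE percentage unclear

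*Combined protocol and SAP*

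**What the plan says.** Section 10.1 lists two primary endpoints, the MTD and "Frequency (number and percentage) of treatment-emergent AEs". A percentage needs a denominator, and three places in Section 10 bear on it:

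- Section 10.3.1 (toxicity): "All patients will be evaluable for toxicity from the time of their first treatment with lenalidomide, romidepsin and CC-486 (5-azacitidine".
- Section 10.3.4 (DLT), of a participant without a DLT who did not finish cycle 1: "they will not be evaluable for toxicity and will be replaced in the dose level".
- Section 10.2 (sample size) gives the same replacement rule with a narrower scope: "they will not be evaluable for determination of the MTD and would be replaced in the dose level".

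The analysis text does not choose between them. Section 10.4.2 says "Reports will include the frequency (number and percentage) of treatment emergent AEs grouped by severity of the AE" without naming a population, and Section 10.4.4 adds none. By contrast, Section 10.4.3 does say which patients must appear in the response reports.

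**The concern.** One group of patients, those who stop in cycle 1 without a DLT, is inside the toxicity set in 10.3.1, outside it in 10.3.4, and outside only the MTD determination in 10.2. An analyst who follows 10.3.4 as written would take treated patients out of a primary safety percentage.

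Those patients need not be free of toxicity. Section 3.2.1 classes grade 3 febrile neutropenia as an SAE but not a DLT. A patient who stopped in cycle 1 after that event, with nothing else that met the DLT definition, would leave the toxicity set under the literal text. Other excepted events, such as qualifying grade 3 neutropenia (3.2.1) or grade 3 rash (3.2.2), could have the same effect.

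The group may also be wider than it looks. Section 3.2 says "Each patient must receive all doses of the investigational medications during cycle 1 to be considered as successfully completing the DLT evaluation period", and Section 3.4.5 records a vomited dose as missed and not given again. If finishing cycle 1 in 10.3.4 is read with Section 3.2, missed doses alone could make a patient a non-completer.

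**Working it through.** **1. The plan's own figures.** For a true DLT rate p, the 3+3 rule in Table 3 escalates with probability

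P = (1−p)³ + 3p(1−p)² × (1−p)³.

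| p | 10% | 20% | 30% | 40% | 50% | 60% |
|---|---|---|---|---|---|---|
| Section 10.2 | 0.91 | 0.71 | 0.49 | 0.31 | 0.17 | 0.08 |
| Recomputed | 0.906 | 0.709 | 0.494 | 0.309 | 0.172 | 0.082 |

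All six agree, including the worked case that "there is a 17% probability of escalating to the next dose". The evaluable totals also reproduce: 3 × 6 + 9 = 27 and 3 × 3 + 9 = 18. These figures use only DLT-evaluable patients, and 10.2 and 10.3.4 treat non-completers alike for that purpose. The contradiction therefore changes none of them.

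**2. Effect on the AE percentage.** Let x of n DLT-evaluable patients have a given AE, and y of m treated non-completers without a DLT.

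- Literal 10.3.4: x/n.
- Section 10.3.1: (x + y)/(n + m).
- Difference, 10.3.1 minus 10.3.4: m/(n + m) × (y/m − x/n).

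The sign depends only on whether the omitted patients had the AE more or less often than the others. With equal rates the difference is zero.

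**3. Illustration at the MTD.** n = 9 comes from Section 10.2. The values x = 5 and m = 1 to 3 are assumptions, because the documents give neither the number of such patients nor their AE rate. Literal 10.3.4 gives 5/9 = 55.6%.

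| Non-completers added (m) | None had the AE | All had the AE |
|---|---|---|
| 1 | 5/10 = 50.0% | 6/10 = 60.0% |
| 2 | 5/11 = 45.5% | 7/11 = 63.6% |
| 3 | 5/12 = 41.7% | 8/12 = 66.7% |

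For m = 2, the formula gives 2/11 × (1 − 5/9) = +8.1 points at one end and 2/11 × (0 − 5/9) = −10.1 points at the other.

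**The case against.** The strongest reply is that this is a one-word slip. Section 10.3.4 is headed as the DLT-evaluable set, its first sentence defines that set, and the disputed sentence gives the complement. Replacement within a dose level belongs to 3+3 cohorts and has no meaning for an AE table. Section 10.2 states the same rule for the MTD alone, and 10.3.1 is the section written for toxicity. AEs are also documented from the first study intervention (6.1.1), whatever their relationship to treatment (8.2), so no data would be lost. This reading is probably right. It tells us how to correct the sentence, but does not remove the contradiction, and 10.4.2 offers nothing to settle it.

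A reader might infer two stronger things that the documents do not support.

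- *That the exclusion makes the regimen look better tolerated.* A DLT is any related toxicity of grade 3 or above outside the listed exceptions (Section 3.2). Table 6 also marks as DLTs any grade 4 AE in cycle 1, and grade 3 platelet or other non-haematological-type events that do not recover after a hold. Patients with a DLT stay in the set, so most who stop for severe related toxicity are not removed. Those who stop early for progression or withdrawal may have had few AEs, and leaving them out would raise the percentage. The febrile neutropenia example is narrower too: it relies on the exception in 3.2.1, which Table 6 does not repeat.
- *That 10% to 25% of treated patients could be lost.* This comes from subtracting 27 from the ceilings of 30 and 36 in Section 10.2 (3/30 and 9/36). Only 36 is tied to unevaluable patients, and it conflicts with the 30 given in the précis and again in 10.2. Section 2.5.1 allows 24 + 6 = 30 evaluable patients, which leaves no gap at 30. A ceiling is also not an expected number of drop-outs.

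**Conclusion.** The contradiction is real, and it affects the denominator of a primary endpoint. It is most likely a wording error, and the documents do not show an intended exclusion from the AE analysis. Followed literally, 10.3.4 would omit some treated patients, possibly including one with a serious related event. The reported percentage could then be too low or too high. The size cannot be estimated from the documents. The range of 45.5% to 63.6% around 55.6% rests on assuming two non-completers and five events among nine evaluable patients. The MTD determination and the sample-size figures stand. The point merits correction before analysis: Section 3.4.1 reports 20 patients enrolled and escalation fully accrued, and the denominator should not be chosen after the results are seen.

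**What to change.** Make three wording changes.

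1. In 10.3.4, say that these participants are *not evaluable for DLT/MTD determination*, matching 10.2, and add that they *remain in the AE analysis set*.
2. In 10.3.1, define that set as *all patients who received at least one dose of any study drug*. The present text joins the three drugs with *and*. Under the original design lenalidomide was given alone for up to seven days (3.4.1), so the status of a patient who stopped in the lead-in is unclear.
3. In 10.4.2, name the 10.3.1 set as the denominator for AE frequencies.

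The cost is a short amendment. No extra patients or data collection are needed, and no stated probability or sample size changes.

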10.4 STATISTICAL ANALYSES

10.4.1 General Approach

The response rate will be determined and reported along with a 95% Agresti-Coull confidence interval [70]. Other time-to-event outcomes will be reported using Kaplan-Meier curves.

10.4.2 Analysis of the Primary Endpoints

Safety summaries will include summaries in the form of tables and listings. Reports will include the frequency (number and percentage) of treatment emergent AEs grouped by severity of the AE (per CTCAE, v5.0) and by relationship to study drug (e.g., lenalidomide, romidepsin, CC-486 (5-azacitidine) in any combinations).

Laboratory shift tables containing counts and percentages will be prepared by treatment assignment, laboratory parameter, and time. Summary tables will be prepared for each laboratory parameter. Figures of changes in laboratory parameters over time will be generated.

Results of vital sign assessments, ECGs, and physical exams will be tabulated and summarized.

10.4.3 Analysis of the Secondary Endpoints

Overall response rate (ORR), complete response (CR) rate will be estimated. Every report of response rates and time to progression should contain all patients included in the study. For the response calculation, the report should contain at least a section with all eligible patients. Another section of the report may detail the response rate for evaluable patients only. However, a response rate analysis based on a subset of patients must explain which patients were excluded and for which reasons. 95% confidence limits will be given.

The duration of response (DOR), overall survival (OS), event-free survival (EFS), and progression free survival (PFS) will be estimated using Kaplan-Meier curves with appropriate confidence intervals reported. For EFS, PFS, and OS, censoring time is defined as time from baseline to date of last follow-up. DOR for responders also calculated using the Kaplan-Meier approach is defined in section [6.3.3](#). Censoring time for duration of response is defined as time from the initial response to date of last follow-up.

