3.8.2 Follow-Up Visits - Prior to Disease Progression

Patients who complete trial treatment without evidence of disease progression will move into the Follow-up Phase and may be assessed every 60 days (\pm 7 days) for 6 months; then every 90 days (\pm 14 days) for 2 years; then every six months (\pm 28 days) for 2 years, then annually (\pm 6 weeks) after finishing treatment by radiologic imaging or other clinical assessments to monitor disease status. Every effort should be made to collect information regarding disease status until the start of new anti-neoplastic therapy, disease progression, death, or end of the study. If the patient cannot return to the Clinical Center for any of these visits, a request will be made to have a local physician or laboratory collect a CBC with differential and send the results. If this is not possible, patients may be assessed by telephone or email for symptoms.

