3.8.3 Follow-Up Visits - Survival/Post-Disease Progression

Once a subject experiences confirmed disease progression or starts a new anti-cancer therapy, the subject moves into the survival follow-up phase and should be contacted (e.g., phone, email, etc.; in-person visit not required) at least every 3 to 6 months to collect information on new anti-cancer treatments received and to assess for survival status until death, withdrawal of consent, or the end of the study, whichever occurs first (see Study Calendar, Section 3.9). Any adverse events which

Abbreviated Title: RAdR for R/R TCM

Version Date: 12/04/2025

are present at the time of discontinuation should be followed in accordance with the safety requirements.

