¹ 30 days (± 7) following last dose of any study drug (via clinic or phone). If initiating new anti-cancer therapy within 30 days after last dose of any study drug, 30-day safety follow-up visit must occur before first dose of new therapy.

² Screening and Baseline evaluations should be performed within 28 days prior to enrollment and dosing, respectively, unless otherwise noted and with the following exceptions: Confirmation of diagnosis (no time limit); HIV antibody, HTLV-1/2 serologies, Hepatitis B surface antigen and Hepatitis C antibody, EKG, TTE, bone marrow aspiration/biopsy and Clonal T-cell receptor rearrangement by PCR (all within 3 months), baseline pregnancy testing (within 10 – 14 days and within 24 hours prior to prescribing lenalidomide) **NOTE:** Any screening tests performed within the specified time frame for baseline do not need to be repeated.

³ To be performed on Day 21 (± 2 days) of Cycles 2, 4, and 6. Confirmatory scans should also be obtained 4 weeks following initial documentation of objective response.

⁴ To be done at end of treatment (30 days after last dose of study treatment; may be combined with 30 day safety follow-up, if timing coincides). If subject to initiate new anti-cancer therapy assessments should occur before the first dose of the new therapy.

⁵ Follow-up to occur about every 60 days (± 7 days) for first 6 months, every 90 days (± 14 days) for 2 years, then every 6 months (± 28 days) for another 2 years and then annually (± 6 weeks) until disease progression or initiation of new anti-cancer therapy.

⁶ After disease progression or initiation of new anti-cancer therapy, contact for survival about every 3 to 6 months (± 4 weeks).

⁷ Pathologic review/confirmation of diagnosis by Laboratory of Pathology, NCI (no time limit). If archival sample is not available or not adequate, a fresh tumor biopsy and/or peripheral blood sample will be obtained.

⁸ Complete medical history at screening/baseline. Interim on study and in follow-up. Disease and social history required only at screening.

⁹ Physical exams to include vitals, weight, and height (screening only).

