6.3.3 Duration of Response

The duration of response (DOR) is measured from the time measurement criteria are met for CR or PR (whichever is recorded first) until the first date that recurrent or progressive disease is objectively documented (taking as reference for progressive disease the smallest measurements recorded since the treatment started), death, or, in the absence of PD, date of last assessment.

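### Section 10.4.3 censors PFS, EFS and DOR at last follow-up, as it does OS, although a follow-up contact need not include a disease assessment; for DOR this also conflicts with Section 6.3.3

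*Combined protocol and SAP*

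**What the plan says.** **Censoring.** Section 10.4.3 states: "For EFS, PFS, and OS, censoring time is defined as time from baseline to date of last follow-up". For DOR it refers to Section 6.3.3 and adds: "Censoring time for duration of response is defined as time from the initial response to date of last follow-up". Section 6.3.3 itself ends DOR at recurrence or progression, "death, or, in the absence of PD, date of last assessment". Sections 6.3.4 to 6.3.6 define EFS, PFS and OS from enrollment and give no censoring rule.

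**Follow-up before progression.** Section 3.8.2 plans visits with imaging or other clinical assessment and asks for every effort to obtain disease status. The calendar in Section 3.9 lists imaging for this phase. If the patient cannot return, "a request will be made to have a local physician or laboratory collect a CBC with differential and send the results". Then: "If this is not possible, patients may be assessed by telephone or email for symptoms". Footnote 5 of the calendar runs this phase "until disease progression or initiation of new anti-cancer therapy".

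**Follow-up after new therapy.** Under Section 3.8.3, a patient who "starts a new anti-cancer therapy, the subject moves into the survival follow-up phase" need not be seen in person. Footnote 6 says: "After disease progression or initiation of new anti-cancer therapy, contact for survival about every 3 to 6 months". Section 3.1 keeps transplant patients in survival follow-up.

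**The concern.** Any contact shows that a patient is alive, so last follow-up is a sound censoring date for OS. The same contact does not show that the patient is free of progression. If PFS, EFS and DOR use that date, a patient can stay in the risk set, counted as event-free, through months in which nobody looked at the disease. The text also leaves room for two analysts to report different PFS and DOR curves from the same data. No test, dose decision or sample size depends on these endpoints. What is at stake is how the secondary efficacy results are read, mainly in the tail of the curves.

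**Working it through.** No figure in the plan depends on the censoring date, so there is nothing to reproduce. The check sets the sections side by side and then sizes the effect with illustrations.

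**1. Endpoint by endpoint**

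| Endpoint | Censoring in 6.3 | Censoring in 10.4.3 | Exposed to blood-count or phone-only visits? | Exposed on the new-therapy route? |
|---|---|---|---|---|
| DOR | last assessment (6.3.3) | last follow-up | yes | yes, on the broad reading |
| PFS | none (6.3.5) | last follow-up | yes | yes, on the broad reading |
| EFS | none (6.3.4) | last follow-up | yes, because progression is an EFS event | no, because alternative therapy is an EFS event |
| OS | none (6.3.6) | last follow-up | no | no |

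The direct conflict is in the DOR row only. Neither term is defined, and Section 3.8.2 uses the verb assess even for a phone check, so 6.3.3 does not fully settle the date.

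**2. Two readings of follow-up.** On the broad reading, any contact counts, including survival-only contact after new therapy. On the narrow reading, only the pre-progression phase counts, and footnote 5 ends it at progression or new therapy. The narrow reading removes the new-therapy problem but not the phone-only one.

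**3. Phone-only visits (both readings; constructed data).** Ten responders; seven progress at months 2, 3, 4, 5, 6, 8 and 10. Three are last scanned at months 4, 6 and 8 and have one phone-only visit 60 days later (the interval in 3.8.2), at months 6, 8 and 10. Kaplan-Meier: S(t) is the product of (1 − d/n), with patients censored in a month still at risk for that month's event.

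| Month | n at risk, last scan | S | n at risk, last contact | S |
|---|---|---|---|---|
| 2 | 10 | 0.900 | 10 | 0.900 |
| 3 | 9 | 0.800 | 9 | 0.800 |
| 4 | 8 | 0.700 | 8 | 0.700 |
| 5 | 6 | 0.583 | 7 | 0.600 |
| 6 | 5 | 0.467 | 6 | 0.500 |
| 8 | 3 | 0.311 | 4 | 0.375 |
| 10 | 1 | 0 | 2 | 0.1875 |

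The median is 6 months under both, taking the first time that S is at most 0.5 (a midpoint convention gives 7 for last contact). At 9 months the rates are 31% and 38%. At 10 months they are 0% and 19%, resting on one or two patients.

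**4. New therapy without progression (broad reading; constructed data).** Same seven progressions. The other three are last scanned at month 2, start new therapy at month 3 and are known alive at month 24. Last contact gives S = 0.50 at month 6 and 0.30 from month 10. Censoring at month 3 gives 0.48 at month 5 and 0 at month 10; censoring at month 2 gives 0.45 and 0. The median is 6 months against 5, and the 12-month rate 30% against 0%.

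**5. If later progression goes unseen.** Simulation with n = 27 (the maximum in 10.2) and exponential PFS. Assumed: a fraction f of those progression-free at month 4 stop disease assessment, and all of these are alive at last contact at month 12.

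| Median PFS | True 12-month PFS | Last contact, f = 10%, 25%, 50% | Last assessment |
|---|---|---|---|
| 4 months (Section 1.6.1) | 0.5^(12/4) = 12.5% | 16%, 22%, 32% | about 13% |
| 8 months (assumed) | 0.5^(12/8) = 35.4% | 39%, 44%, 53% | about 36% |

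**6. If deaths after the switch count as events (broad reading).** Progression median 4 months; patients leave without progression between months 1 and 4; survival after the switch has a median of 3.7 or 6.5 months. Those two figures are from Section 1.2.3 and were measured after recurrence or progression, so they are only a stand-in. The shares leaving are assumed. Censoring at the switch gives a median of 4.0 months and a 12-month rate of 12.5%.

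| Share leaving | Median, last contact (months) | 12-month rate, last contact |
|---|---|---|
| 5% | 4.0 | 12-13% |
| 23% | 4.0-4.2 | 12-16% |
| 39% | 3.95-4.5 | 12-19% |

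Within one simulated trial (n = 27, 23% leaving), the difference, last contact minus censored at the switch, had these 5th to 95th percentiles:

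- survival 3.7 months: median −1.5 to +0.9 months; 12-month rate −7 to +7 points
- survival 6.5 months: median −0.9 to +1.5 months; 12-month rate −4 to +13 points

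**7. Sampling noise.** The 95% sampling range of a 4-month median at n = 27 is 2.2 to 6.6 months.

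**The case against.** Four objections carry weight.

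- **Scope of the contradiction.** A reader might infer that two sections contradict each other on PFS. They do not: 6.3.5 has no censoring rule, so for PFS and EFS the complaint is that the only rule uses an unsuitable, undefined date. For DOR, one can argue that 6.3.3 controls because 10.4.3 cites it and its sentence concerns objectively documented progression. That is a sensible reading, but 10.4.3 then states a different date in its own words, so the conflict stands.
- **The fallback is a fallback.** Imaging or clinical assessment is planned, and the blood count and the phone or email check apply only when the patient cannot return. The documents do not support inferring that remote contact is the planned way of following these patients. The two dates differ only for patients with such contacts, new therapy or transplant. However, Section 1.10.2 presents the regimen partly as a bridge to transplant, so some patients leaving without progression are expected.
- **The narrow reading is natural.** The calendar separates pre-progression follow-up from survival contact. But the heading of 3.8.3 also calls the latter follow-up visits, so the ambiguity remains.
- **The sizes are built on assumptions.** This stands. The shares leaving are not in the documents, and the upward shifts in step 5 assume that nobody who leaves dies before month 12, although death is a PFS event.

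**Conclusion.** The point holds and is minor. Section 10.4.3 lets time without disease assessment count as progression-free, event-free or in response, and for DOR it disagrees with the section it cites. OS is unaffected.

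Two further inferences are tempting and unsupported. One is that the rule inflates PFS and DOR. It does so when later progression goes unseen and the patient stays alive, but when deaths after a switch count as events the difference can go either way. The other is that EFS is safe because alternative therapy is an EFS event. That protects it on the new-therapy route only; a phone-only visit affects EFS as it affects PFS.

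The endpoints are secondary and descriptive. In the scenario that uses the documents' own survival figures, 5% leaving makes a negligible difference, and the shifts in the median at 23% or 39% are small against a sampling range of 2.2 to 6.6 months. The wording conflict is certain; the size and direction in this trial cannot be known from the documents.

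**What to change.** Put one rule in Sections 10.4.3 and 6.3.3:

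> Patients without an event are censored for PFS, EFS and DOR at the last adequate disease assessment (imaging, or the skin or blood assessment that applies to the disease, Section 6.3). A phone or email symptom check, a survival-only contact, or a CBC that is not the applicable blood assessment does not count. OS is censored at the date last known alive. PFS, EFS and OS run from enrollment (6.3.4-6.3.6).

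The last sentence also replaces the undefined baseline from which 10.4.3 counts.

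Before the analysis, also:

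- State how new therapy or transplant without progression is handled for PFS and DOR. Censoring at the last assessment before it and following patients through it are both defensible; run the other as a sensitivity analysis. Say whether transplant counts as alternative therapy for EFS.
- Reconcile Section 6.3.1.2, which uses the off-treatment date for TTP and/or DOR in CTCL without saying whether it is an event or a censoring. This matters only for CTCL patients already treated, because the expansion cohort excludes CTCL.

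**Cost.** Wording only; assessment and contact dates are already collected. The price is somewhat less follow-up time and possible informative censoring. In an illustration where only the better-prognosis half leaves (progression medians 12 and 4 months, 26% leaving), censoring at the switch gives a median of 5.8 months against 6.6 for underlying progression. Following patients through transplant is limited to whatever disease data exist, because disease status is not systematically sought after new therapy.
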